### 10.2 Secondary study parameter(s)

Differences in change between intervention and control group regarding mean glucose and glycemic variability from CGM, BMI and body weight, waist circumference, breath hydrogen and serum GLP-1/PYY and SCFA levels will be analysed using similar methods as the primary study parameters.

The data on microbiota composition will be analysed by the Laboratory of Microbiology (prof. [name]) according to established methods (Korpela et al., 2014). Data on wellbeing, i.e. hunger feelings, adverse events (bloating, belching, flatulence and frequency and consistence of faeces by means of the Bristol Stool Chart (Lewis and Heaton, 1997)) will be derived from the wellbeing diary. The data will be expressed as number of days with complaints, and will be compared between the intervention and control group using non-parametric statistics.

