#### 8.1.2 Secondary study parameters/endpoints (if applicable)

- Continuous Glucose Monitoring (CGM): mean glucose and glycemc variability
- Body weight
- Waist circumference
- Microbiota composition
- Breath hydrogen
- Fasting GLP-1/PYY
- Fasting SCFA
- Adverse events (bloating, belching, flatulence)

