### 8.3 Study procedures

The volunteers will have a pre-study screening before the start of the intervention. This will involve:

- assessment of medical history
- assessment of Diabetes Risk Score (kijkopdiabetes.nl)
- assessment of regular fibre intake measured with a specific food frequency questionnaire
- measuring height, weight, waist circumference
- measuring fasting glucose from finger prick

For the timing of the procedure, see Table 1 in the Chapter Study Design. For logistic reasons subjects will be divided in two groups, starting their treatment period on two consecutive days. For both series the first day of treatment will be specified as Day 01.

During the main part of the intervention the subjects will consume 30 grams of WF fibre or 16 grams of placebo per day, for 21 consecutive days. Before starting, a fasting venous blood sample (total 30ml) will be taken to determine fasting blood glucose and insulin concentrations, and body weight and waist circumference will be measured. Subjects are asked to provide a stool sample for microbiota determination. For this, the participants will receive a home sampling kit with instructions from the WU Laboratory of Microbiology. Also a continuous blood glucose meter will be placed. Also a fasting breath sample will be obtained.

A run in period of 2 weeks on 15 gram WF fibre or 8 grams of placebo will precede the trial to avoid gastro-intestinal discomfort. After that, and before starting the main phase of the intervention, another stool sample will be asked for.

After 21 days of intervention with the full dose, a fasting blood sample, a stool sample, a breath sample and data on body composition will be obtained. After another 14 days of wash-out a final stool sample will be obtained. During the 49 days study period (2+3+2 weeks of run-in, intervention and wash-out resp.) a diary on abdominal side effects will be kept.

Compliance will be assessed by asking subjects to return unused and opened non-empty sachets.

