## 10. STATISTICAL ANALYSIS

The statistical analyses will be carried out by SPSS (Version23; 2015, IBM SPSS Statistics) or a comparable software program. Statistical test will be done two-sided with a significance level of 5%. Normality will be checked for all continuous outcome variables by inspecting Q-Q plots.

For the descriptive analyses results will be presented as mean  $\pm$  SD, or median and interquartile range, or percentage, depending on their distribution.

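### Section 10.2 summarises stool form, stool frequency and hunger as complaint days, a measure that can lose direction for the first two and loses grade for the third (minor)

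*Protocol*

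**What the plan says.** Section 10.2 describes the diary content as "Data on wellbeing, i.e. hunger feelings, adverse events (bloating, belching", followed by flatulence and by "frequency and consistence of faeces by means of the Bristol Stool Chart". The next sentence gives the measure: "The data will be expressed as number of days with complaints". These data "will be compared between the intervention and control group using non-parametric statistics". No other measure is given for stool consistency, stool frequency or hunger, and the section does not say what makes a day a complaint day for them.

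Two other places bear on the point. The secondary endpoint list in section 8.1.2 names "Adverse events (bloating, belching, flatulence" and no further diary item. Section 8.3 gives the diary's purpose and length: "During the 49 days study period (2+3+2 weeks of run-in, intervention and wash-out resp.) a diary on abdominal side effects will be kept".

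**The concern.** Bloating, belching and flatulence are unwanted and run one way, so counting the days on which they occur is a sensible summary. The other three items are different in kind.

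- **Stool form.** The Bristol chart is an ordinal scale whose two ends are both abnormal. Moving from hard to normal and moving from normal to loose are both softening, but the first removes complaint days and the second adds them. If both ends feed one count, the two effects offset each other.
- **Stool frequency.** This is a count that can be too low or too high, so the same offsetting can occur.
- **Hunger.** This is a feeling of varying strength and is not in itself a complaint. The Introduction cites short-term effects of fibre on satiety, so less hunger is a plausible effect of the product. A count of complaint days does not show its degree.

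At stake is whether the trial can report from its own diary that the fibre changed bowel habit, and in which direction. The primary analysis is not affected.

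**Working it through.** **Inputs from the protocol.** 27 evaluable subjects per arm (section 4.5: 54 in total, and 54/0.9 = 60 randomised); 21 full-dose days (section 3); two-sided 5% level (section 10); a non-parametric comparison (section 10.2). The protocol gives no figure for any diary outcome, so there is none to reproduce.

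**Assumed inputs.** The protocol gives no distribution for stool form and no definition of a complaint day. I assume normally distributed daily scores and count types 1-2 and 6-7 as complaints, which puts the cut-offs at 2.5 and 5.5.

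**Step 1: direct calculation, SD 1.2.**

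- Control, mean 3.5: P(hard) = P(Z < (2.5 - 3.5)/1.2) = P(Z < -0.833) = 20.2%. P(loose) = P(Z > (5.5 - 3.5)/1.2) = P(Z > 1.667) = 4.8%. Sum 25.0%.
- Fibre, mean 4.5: P(hard) = P(Z < -1.667) = 4.8%. P(loose) = P(Z > 0.833) = 20.2%. Sum 25.0%.

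The difference in complaint days is zero, although every stool has moved by one point and loose-stool days have risen about fourfold (20.2/4.8 = 4.2).

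**Step 2: simulation.** 2,000 trials per scenario, 27 per arm, 21 days; between-person SD 0.7 and within-person SD 1.0 (combined √(0.49 + 1.00) = 1.22); scores rounded to 1-7. Each trial was tested by Mann-Whitney on complaint days and on the subject's mean Bristol type.

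| Mean type, control → fibre | Complaint days, control / fibre | Rejection, complaint days | Rejection, mean type |
|---|---|---|---|
| 3.5 → 3.5 (no effect) | 5.4 / 5.4 | 5% | 5% |
| 3.5 → 4.5 | 5.4 / 5.4 | 5% | >99% |
| 3.6 → 4.4 | 5.1 / 5.1 | 5% | 96% |
| 3.5 → 4.0 | 5.4 / 4.6 | 12% | 65% |
| 3.0 → 3.6 | 7.6 / 5.2 | 54% | 80% |
| 3.0 → 4.0 | 7.6 / 4.6 | 74% | >99% |
| 4.0 → 5.0 | 4.6 / 7.6 | 73% | >99% |

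In the 3.5 → 4.5 row, hard-stool days fall from 4.3 to 1.1 and loose-stool days rise from 1.1 to 4.3. The last two rows show the loss of direction. Both are a one-point softening, yet the count falls by about 3 days in one and rises by about 3 in the other.

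**Step 3: stool frequency.** Daily counts were simulated as Poisson with between-person variation, with 0 or more than 3 stools in a day assumed to be a complaint. From 1.5 to 2.2 stools per day, complaint days are 7.0 and 7.2; the count rejects in 5% of trials and mean stools per day in 93%. From 1.0 to 1.5 the figures are 56% and 93%.

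**Hunger.** No scale is described, so no calculation is possible. The argument there is loss of grade only.

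**The case against.** The strongest reply is that the diary is a tolerability instrument. Section 8.3 describes it as a record of abdominal side effects, and section 10.2 places stool frequency and consistency within the adverse-event items. Days with a complaint is a natural measure for that purpose. Stool form, stool frequency and hunger appear neither in the objectives nor in section 8.1.2, and laxation benefit is not a trial objective. This stands, and it is why the point is minor.

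Second, the cancellation rests on assumptions. The protocol does not say that hard and loose stools share one count. Counts kept separately for each complaint would preserve direction. Means of 3.5 and 4.5 lie symmetrically about type 4, which forces the zero. This also stands: full cancellation is a special case, and the example shows what the measure can do, not what it will do. It does not remove the point, because the sentence still gives complaint days as the only measure for all the items. If it was meant for the complaint items alone, the other three have no stated measure.

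Third, a reader might infer that the count runs over all 49 diary days, so that 14 off-product days (14/49 = 29%) dilute 21 full-dose days (21/49 = 43%). The documents do not support this. Section 8.3 says only how long the diary is kept, Table 1 schedules it by phase, and nothing says the phases are pooled. The counting window is simply not named.

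Finally, definitions of individual complaints are often left to an analysis plan, which is not shown here. That is fair for cut-offs. The choice of complaint days as the measure, however, is made in the protocol itself.

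**Conclusion.** The point holds as a minor one. Read as written, section 10.2 applies to stool form, stool frequency and hunger a measure that fits only bloating, belching and flatulence. For stool form and frequency, if both abnormal directions enter one count, the sign of a difference no longer shows which way bowel habit moved. Under the assumed distributions, the chance of detecting a stool-form shift falls to 5% (the false-positive rate) in the symmetric cases and to 12-74% in the off-centre ones, against 65% to over 99% for mean type. For hunger the loss is of grade, and the two-directional argument does not extend to it.

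These sizes depend on the assumed means, SDs and complaint cut-offs and on counting hard and loose days together, none of which the protocol specifies. It would be too strong to say that the plan will miss an effect on bowel habit, or that its conclusions on bloating, belching and flatulence are compromised.

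**What to change.** Rewrite the diary paragraph in section 10.2 as follows:

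1. Keep complaint days for bloating, belching and flatulence.
2. Summarise stool form as days (or percentage of recorded stools) with types 1-2 and, separately, types 6-7, together with mean type.
3. Summarise stool frequency as stools per day.
4. Summarise hunger on the scale recorded in the diary.
5. Compare the arms with the non-parametric tests already planned.

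As a clarification only, name the 21-day full-dose phase as the comparison window.

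The cost is one paragraph and a few more comparisons on minor, non-primary outcomes. No extra visits or measurements are needed, provided that the diary form, which is not shown, records Bristol type, the number of stools and a graded hunger item. That should be checked before the text is changed.

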### 10.3 Other study parameters

Age, gender, body height, cigarette smoking, highest education level, family history of diabetes; for women, history of gestational diabetes will be described by intervention/control group, using descriptive statistics, to characterise the study population.

### 10.4 Interim analysis (if applicable)

Not applicable.

## 11. ETHICAL CONSIDERATIONS

### 11.1 Regulation statement

The study will be conducted according to the principles of the Declaration of Helsinki (Fortaleza, Brasil 2013) and in accordance with the Medical Research Involving Human Subjects Act (WMO).

### 11.2 Recruitment and consent

The focus of the recruitment will be on the database of volunteers of our department HNE, with inclusion of participants of an earlier longitudinal observational study NQplus. An invitation to participate will be sent to all subjects with reference to the age range. Subjects that are willing to participate will receive the information brochure including an informed consent and are invited for information meeting on the study. The informed consent must be signed in at the screening visit. The subject will sign the informed consent first, followed by the research assistant (in such a way that the subject can visually establish that the investigator does not change anything on the form after he/she signed it), and the subject will receive a copy of the informed consent form directly after the signing.

Personal data will be stored in a closed locker and a password-protected file, to which only the database manager (or his/her replacement) has access.

All the data will be destroyed 15 years after finishing the study.

### 11.3 Benefits and risks assessment, group relatedness

- To increase the fibre intake
- To decrease the number of diabetes patients
- To get information about some of their health outcomes; glucose levels, insulin levels and microbiota composition
- The intervention is therapeutic to the participants in the intervention group. The fibre intake including the 30g WF does not exceed 75g, a dose which may lead to uncomfortable side effects. Uncomfortable side effects as bloating and flatulence sometimes occur after ingestion of some types of fibre, they are however harmless. Participants are informed on these possible side effects beforehand. As the fibres used in the study are safe to use for human consumption the risk associated with participation is negligible and the burden can be considered moderate.
- Venapunctures can occasionally cause a local hematoma or bruise and some participants may report pain or discomfort. Placing the continuous glucose meter can cause minimal pain or discomfort.
- Screening visit 20 min, baseline visit 30 min, endline visit 30 min, questionnaires at home, total 60 min.

### **11.4 Compensation for injury**

Wageningen University has a liability insurance which is in accordance with article 7, of the WMO.

Wageningen University (also) has an insurance which is in accordance with the legal requirements in the Netherlands (Article 7 WMO and the Measure regarding Compulsory Insurance for Clinical Research in Humans of 24 November 2014). This insurance provides cover for damage to research subjects through injury or death caused by the study.

1. € 650.000,-- (i.e. six hundred and fifty thousand Euro) for death or injury for each subject who participates in the Research;
2. € 5.000.000,-- (i.e. five million Euro) for death or injury for all subjects who participate in the Research;
3. € 7.500.000,-- (i.e. seven million five hundred thousand Euro) for the total damage incurred by the organisation for all damage disclosed by scientific research for the Sponsor as 'verrichter' in the meaning of said Act in each year of insurance coverage.

The insurance applies to the damage that becomes apparent during the study or within 4 years after the end of the study.

Wageningen University has this insurance at:

HDI- Global SE, the Netherlands

[name]

[name]

### **11.6 Incentives (if applicable)**

Participants will receive €200,- after completing the study. When participant withdraw during the study they receive an incentive in proportion to the duration of the study.

## **12. ADMINISTRATIVE ASPECTS, MONITORING AND PUBLICATION**

### **12.1 Handling and storage of data and documents**

All data will be handled confidentially. Data will be stored in a password protected file. Only members of the project team can access this file. The informed consents will be stored separately from all other information. Human material, which is sampled during the study will be stored anonymously. All human material will be stored for 15 years after finishing the study.

### **12.2 Amendments**

A 'substantial amendment' is defined as an amendment to the terms of the METC application, or to the protocol or any other supporting documentation, that is likely to affect to a significant degree:

- the safety or physical or mental integrity of the subjects of the trial;
- the scientific value of the trial;
- the conduct or management of the trial; or
- the quality or safety of any intervention used in the trial.

All substantial amendments will be notified to the METC and to the competent authority.

Non-substantial amendments will not be notified to the accredited METC and the competent authority, but will be recorded and filed by the sponsor.

### **12.3 Annual progress report**

Not applicable

### **12.4 End of study report**

The sponsor will notify the accredited METC and the competent authority of the end of the study within a period of 8 weeks. The end of the study is defined as the last patient's last visit. If the end of study is defined otherwise, this new definition should be given.

In case the study is ended prematurely, the sponsor will notify the accredited METC and the competent authority within 15 days, including the reasons for the premature termination.

Within one year after the end of the study, the investigator/sponsor will submit a final study report with the results of the study, including any publications/abstracts of the study, to the accredited METC.

**12.5 Public disclosure and publication policy**

Results will be presented in agreement with the CCMO publication statement.

## **13. STRUCTURED RISK ANALYSIS**

### **13.1 Potential issues of concern**

Not applicable

### **13.2 Synthesis**

Not applicable

